#### **Reporting to FDA:**

- Serious adverse events will be forwarded to FDA by the IND Sponsor (Safety Project Manager IND Office) according to 21 CFR 312.32.

**It is the responsibility of the PI and the research team to ensure serious adverse events are reported according to the Code of Federal Regulations, Good Clinical Practices, the protocol guidelines, the sponsor’s guidelines, and Institutional Review Board policy.**

#### **G. Expedited Reporting**

Eisai, Inc. must inform Investigators and regulatory authorities of reportable events, in compliance with applicable regulatory requirements, on an expedited basis (i.e., within specific timeframes). For this reason, it is imperative that investigational sites provide complete SAE information in the manner described above.

- H. An Unexpected Adverse Event** is one that is not listed in the current Clinical Investigator’s Brochure (CIB) / Package Insert or that differs from the event mentioned in the CIB / Package Insert because of greater severity or specificity.

**Causality** is a determination of whether there is a reasonable possibility that the drug may have caused or contributed to an adverse event. It includes assessing temporal relationships, dechallenge/rechallenge information, association (or lack of

association) with underlying diseases, and the presence (or absence) of one or more likely causes.

The investigator must attempt to determine whether an adverse event is in some way related to the use of the study drug. This relationship should be described as follows:

**Unlikely:** The event is clearly due to causes distinct from the use of the study drug, such as a documented pre-existing condition, the effect of a concomitant medication, or a new condition that, based on the pathophysiology of the condition and the pharmacology of the study drug, is unlikely to be related to the use of the study drug.

**Possible:** The event follows a reasonable temporal sequence from administration of the study drug or the event follows a known response pattern to the study drug, *but* the event could have been produced by a concomitant medication or an intercurrent medical condition which, based on the pathophysiology of the condition and the pharmacology of the study drug, is unlikely to be related to the use of the study drug.

**Probable:** The event follows a reasonable temporal sequence from administration of the study drug and the event follows a known response pattern to the study drug and the event cannot be reasonably explained by an intercurrent medical condition or the event cannot be the effect of a concomitant medication.

**Definite:** The event follows a reasonable temporal sequence from administration of the study drug, the event follows a known response pattern to the study drug, and based on the known pharmacology of the study drug, the event is clearly related to the effect of the study drug.

**Unknown:** Based on the evidence available, causality cannot be ascribed.

Please see Appendix G regarding data capturing of adverse events and adverse events source documentation.

## **XVI. DRUG ACCOUNTABILITY**

The Investigator and study staff will be responsible for the accountability of all clinical supplies (dispensing, inventory, and record keeping) following Eisai, Inc. instructions and adhere to GCP guidelines as well as local and / or regional requirements.

Under no circumstances will the Investigator allow the study drug to be used other than as directed by this protocol. Clinical supplies will not be administered to any individual who is not enrolled in the study.

An accurate and timely record of the receipt of all clinical supplies, administration of study drug to the subject, and subsequent destruction of all used and unused study

drug must be maintained. This includes, but may not be limited to: (a) documentation of receipt of clinical supplies, (b) study drug dispensing/return reconciliation log, (unused vials will be shipped back, all used vials should be destroyed on-site per MDACC institutional policy) (c) study drug accountability log, and (d) all shipping service receipts. All forms will be provided by Eisai, Inc. Any comparable forms that the investigational site wishes to use must be approved by Eisai, Inc.

The supplies and inventory records must be made available, upon request, for inspection by the designated representative of Eisai, Inc., a representative of the Food and Drug Administration, or a representative of a non-U.S. health authority. All used and unused study drug, including empty containers, are to be accounted for and destroyed according to site policy and procedure throughout the course of the trial.

The CRAs will review drug accountability during investigational site visits and at the completion of the study.

## **XVIII. ETHICAL AND REGULATORY STANDARDS**

### **Ethical Principles**

The study will be conducted according to the principles outlined by the 18th World Medical Assembly (Helsinki, 1964) and all applicable amendments; the International Conference on Harmonization Guidelines for Good Clinical Practice; and FDA regulations regarding the conduct of clinical trials and the protection of human subjects.

### **Informed Consent**

It is the responsibility of the Investigator to obtain written informed consent from a patient or a patient's legal representative before any study-related procedures are performed. The Investigator will provide an informed consent in compliance with ICH, GCP, and U.S. FDA guidelines (21 CFR 50). The informed consent document must clearly describe the potential

risks and benefits of the trial, and each prospective participant must be given adequate time to discuss the trial with the Investigator or site staff and to decide whether or not to participate. The informed consent must be approved by the IRB prior to being presented to a potential patient.

One copy of the patient's signed, dated, and witnessed written consent will be kept in the patient's medical record, and one copy will be given to the patient or the patient's legal representative.

### **Institutional Review Board (IRB) Approval**

The Investigator must obtain approval of the protocol, the informed consent document, and any other material used to inform the patient about the nature of the trial from the local IRB in the form of a written letter. In the approval letter, which must be signed by the Chairperson of the IRB or the Chairperson's designee, the following items should be clearly stated: trial title, protocol number and version, study-related documents (protocol, informed consent material, advertisement when applicable), IRB review date, and IRB decision. The trial should not start until a copy of this written approval has been received by the Investigator.

If the Investigator is a member of the IRB, the Investigator may participate in any discussion of the study but may not participate in the final vote deciding whether to approve the study.

Annually, or more often if stipulated by the IRB, and at the completion or termination of the study, the Investigator will report the progress of the trial to the IRB.

### **Additional Responsibilities of the Investigator**

The Investigator(s) agrees to perform the study in accordance with ICH Good Clinical Practice and FDA regulations. The Investigator is required to ensure compliance with respect to the investigational drug schedule, visit schedule, and procedures required by the protocol.

The Investigator should be able to recruit the required number of suitable patients and should have sufficient time to properly conduct and complete the trial. The Investigator should have available an adequate number of qualified staff and adequate facilities for the duration of the trial and should ensure that all persons assisting with the trial are adequately informed about the protocol, the protocol-defined procedures, protocol therapy, and trial-related duties and functions.

The Investigator should be responsible for all trial-related medical decisions. During and following a patient's participation in a trial, the investigator should ensure that adequate medical care is provided to a patient for any adverse events related to the trial.

### **Confidentiality**

It is the responsibility of the Investigator to ensure that the confidentiality of all patients participating in the trial and all of their medical information is maintained. Case report forms must never contain the name of a trial patient. All case report forms and any identifying information must be kept in a secure location, with access limited to the study staff directly participating in the trial. Personal medical information may be reviewed by a representative of Eisai, Inc., of the IRB, or of regulatory authorities in the course of auditing the trial. Every reasonable effort will be made to maintain such information as confidential.

## **XIX. LABORATORY TESTS**

All labs for eligibility determination and bone marrow aspirations and/or biopsy for disease evaluation will be done at MD Anderson Cancer Center. Safety labs and Long Term Follow-up labs may be done with patients' local physician. See Section XI.

## **XX. STATISTICAL CONSIDERATIONS**

The objective of this study is to assess the efficacy and safety of treatment of E7070 with chemotherapy in Leukemia patients. The efficacy will be measured by the overall response (CR + CRp + PR+ marrow clearance of blast) during Cycle 1. The sample size and stopping rules will be determined according to Simon's two-stage design.

The efficacy will be assessed based on the Simon's two-stage Minmax design. The new treatment will be considered promising if the response rate is 25% or higher, and will be considered unworthy of further investigation if response rate is 10% or less. The maximum sample size of 40 patients is chosen to differentiate between response rates of 10% and 25% with 90% power at a significance level of 0.1. In particular, 27 patients will be enrolled at the first stage. If there are two or fewer patients with response, the trial will be terminated; otherwise another 13 patients will be treated for a total of 40 patients. If, among 40 patients, there are 6 or fewer patients with response, the treatment will be concluded ineffective. The probability of early termination due to futility is 0.48.

A Bayesian sequential monitoring method will be used to monitor the toxicity. We stop the trial if the toxicity is likely to be greater than 33%. That is, stop the trial if

$$\text{Prob \{toxicity rate > 33\% | data\}} > 0.80.$$

The prior distribution of toxicity rate is assumed to be beta (0.67, 1.33). Following this rule, the trial will be terminated due to toxicity if  $[\# \text{ toxicity}]/[\# \text{ patients evaluated}] \geq 2/3, 3/5, 4/7, 5/10, 6/13, 7/15, 8/18, 9/20, 10/23, 11/26, 12/28, 13/31, 14/34, 15/37, \text{ or } 16/40$ .

A toxic event will be defined as death or a CTCAE 4.0 grade 3/4 non-hematological toxicity related to study drug lasting or 7 days or more.

Descriptive statistical analysis will be calculated, including histograms or box-plots, proportions, range, means and standard deviations. Fisher's exact test and Wilcoxon rank test will be used in univariate analyses of categorical and continuous variables, respectively. Overall response (CR + CRp + PR) rate and its 95% confidence interval will be estimated using a binomial distribution. Overall survival and progression free survival functions will be estimated using the Kaplan-Meier method. The two-sided log-rank test will be used to examine the difference of survival functions among different groups. Toxicity will be reported by type, frequency and severity. Worst toxicity grades per patient will be tabulated for selected adverse events and laboratory measurements.

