## I. OBJECTIVES

### Primary Objectives

1. To assess the complete response (CR) and CR with incomplete platelet recovery (CRp) rates with combination therapy of E7070, idarubicin and cytarabine in patients with relapsed or refractory acute myeloid leukemia (AML) or high-risk myelodysplastic syndromes (HRMDS), and.
2. To determine the safety and toxicity profile of combination therapy with combination therapy of E7070, idarubicin and cytarabine in patients with relapsed or refractory AML or HRMDS.

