##### A. Treatment Plan

[figure not shown]
E7070 400 mg/m^2 intravenously (IV) approximately over 1 hour on day 1 and day 8 (± 2 days on Day 8 only) followed by:

- Idarubicin 8 mg/m^2 IV approximately over 1 hour daily x 3 (days 9-11) and
- Cytarabine 1.0 g/m^2 IV approximately over 24 hours daily on day 9-12 (age <60 years) or days 9-11 (age ≥ 60 years).
- Dexamethasone 10 mg IV daily for 3-4 days with cytarabine

Variations in infusion times due to minor differences in IV bag overfill/underfill and institutional procedure on flushing chemotherapy lines will not result in protocol deviation.

Patient will undergo disease assessment on day 28 ± 3 days at the discretion of treating physician. This assessment can be repeated or delayed at the discretion of treating physician if there is ground to believe that the patient is benefiting from study drug. Patients who derive clinical benefit e.g. CR, CRp, PR or marrow clearance of blasts may receive up to two additional cycles of E7070 in combination with chemotherapy at the above doses. Each cycle will be approximately 28 days (+/- 2 days). Dose modifications and delays are allowed for persistent cytopenias or non-hematological toxicities.

Patients not achieving less than an objective response after cycle 1 may receive another cycle of therapy if considered to be in best interest by investigator. If such a patient achieves an objective response as defined in response criteria after the second cycle may receive one more cycle of therapy on study. If a patient does not achieve an objective response after two cycles of therapy, the patient will be removed from study for lack of response.

**B. Dose modification** will be according to Table 1:

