 To include glucose, total protein, albumin, electrolytes [sodium, potassium, chloride, CO2], calcium, phosphorus, magnesium, uric acid, bilirubin (total, direct), SGPT (ALT) or SGOT (AST), alkaline phosphatase, lactate dehydrogenase, creatinine, blood urea nitrogen will be performed at least weekly.

 Creatinine, total bilirubin, electrolytes, AST and/or ALT once every week during Cycle 1, then every 2-4 weeks during Cycles 2-3.

 Within one month, to include cytogenetics, unless these tests were done within 3 months.

 And as indicated until documentation of response. Bone marrow examinations may be omitted in patients where there is clear evidence of active disease (e.g., increasing blasts in peripheral blood)

 At or within 1 month of screening

 Done at least 1 hour after completion of E7070 infusion if EKG is done on the day of the E7070 infusion day

 For women of childbearing potential within 7 days prior to day 1

 If patient is found to be CR, CRp, PR or marrow clearance of blasts, may receive up to 2 additional cycles of E7070 in combination with chemotherapy

 To include vital signs and weight

 Approximately every 28 days to 2 additional cycles

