### XIII. CRITERIA FOR RESPONSE FOR ACUTE LEUKEMIAS AND MDS

International Working Group Criteria will be used to define response.

1. Complete remission (CR): The patient must be free of all symptoms related to leukemia and have an absolute neutrophil count  $\geq 1.0 \times 10^9/L$ , platelet count  $\geq 100 \times 10^9/L$ , and normal bone marrow differential ( $\leq 5\%$  blasts).
2. Complete remission without platelet recovery (CRp): As per CR but platelet count  $< 100 \times 10^9/L$ .
3. Partial remission (PR): CR with 6 to 25% abnormal cells in the marrow or 50% decrease in bone marrow blasts.
4. Marrow CR: Bone marrow:  $\leq 5\%$  myeloblasts and decrease by  $\geq 50\%$  over pre-treatment (MDS only)
5. Morphologic leukemia-free state: Normal marrow differential ( $< 5\%$  blasts); neutrophil and platelet counts are not considered. (AML only)
6. Hematologic Improvement (HI): HI should be described by the number of individual, positively affected cell lines (e.g. HI-E; HI-E + HI-N; HI-E + HI-P + HI-N)
  - a) Erythroid response (HI-E):
    - Major response: For patients with pretreatment hemoglobin less than 11 g/dL, greater than 2 g/dL increase in hemoglobin; for RBC transfusion-dependent subjects, transfusion independence.
    - Minor response: For patients with pretreatment hemoglobin less than 11 g/dL, 1 to 2 g/dL increase in hemoglobin; for RBC transfusion-dependent patients, 50% decrease in transfusion requirements.
  - b) Platelet response (HI-P):
    - Major response: For patients with a pretreatment platelet count less than  $100 \times 10^9/L$ , an absolute increase of  $30 \times 10^9/L$  or more; for platelet transfusion-dependent patients, stabilization of platelet transfusion independence.
    - Minor response: For patients with a pretreatment platelet count less than  $100 \times 10^9/L$ , a 50% or more increase in platelet count with a net increase greater than  $10 \times 10^9/L$  but less than  $30 \times 10^9/L$ .
  - c) Neutrophil response (HI-N):
    - Major response: For absolute neutrophil count (ANC) less than  $1.5 \times 10^9/L$  before therapy, at least a 100% increase, or an absolute increase of more than  $0.5 \times 10^9/L$ , whichever is greater.
    - Minor response: For ANC less than  $1.5 \times 10^9/L$  before therapy, ANC increase of at least 100%, but absolute increase less than  $0.5 \times 10^9/L$ .

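### The Simon rule counts a broader response than the CR/CRp primary objective, so a promising result carries no type I error control for CR+CRp, and the planned interval uses a third definition

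*Combined protocol and SAP*

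**What the plan says.** Three places define the response of interest, and each defines it differently.

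- **Objective** (synopsis and Section I, first primary objective): "To assess the complete response (CR) and CR with incomplete platelet recovery (CRp) rates with combination therapy of E7070, idarubicin and cytarabine".
- **Decision rule** (Section XX, opening paragraph): "The efficacy will be measured by the overall response (CR + CRp + PR+ marrow clearance of blast) during Cycle 1". The Simon minimax rule follows: stop at 2 or fewer responses in 27, and conclude ineffective at 6 or fewer in 40, for rates of 10% against 25%.
- **Estimate** (Section XX, closing paragraph): "Overall response (CR + CRp + PR) rate and its 95% confidence interval will be estimated using a binomial distribution".

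Three other places bear on what is counted.

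- Section XIII has no entry called marrow clearance. The nearest are marrow CR (MDS only) and, for AML only, "Morphologic leukemia-free state: Normal marrow differential".
- Section XIII describes PR as "CR with 6 to 25% abnormal cells in the marrow or 50% decrease in bone marrow blasts".
- Section IV.A says of the day 28 evaluation: "This assessment can be repeated or delayed at the discretion of treating physician". It also provides for a patient who "achieves an objective response as defined in response criteria after the second cycle".

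**The concern.** The trial's one formal efficacy decision is made on an endpoint that the objectives do not name. CR and CRp can appear among the descriptive proportions in Section XX, but they have no threshold and no interval. If some patients reach only PR or marrow clearance, the regimen can be declared promising without any bound on how often that happens when CR+CRp is no better than the rate the plan itself calls unworthy of further study. The published rate and interval may also describe a different set of patients from the one that drove the decision, although Section XX uses the same term for both. If no patient has PR or marrow clearance alone, the three counts agree and nothing is lost.

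**Working it through.** **Inputs.** From Section XX: n1 = 27, r1 = 2, n = 40 (27 + 13), r = 6, unworthy rate 0.10, promising rate 0.25, significance level 0.1, power 90%, early termination 0.48. Assumed: d, the percentage of patients with PR or marrow clearance but neither CR nor CRp. The documents give no value for d, so a range is shown.

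**1. Reproduce the design.** With X1 ~ Bin(27, p) and X2 ~ Bin(13, p):

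- P(early stop) = P(X1 ≤ 2). At p = 0.10: 0.9^27 + 27(0.1)(0.9^26) + 351(0.01)(0.9^25) = 0.0582 + 0.1744 + 0.2520 = 0.4846. The plan states 0.48.
- P(promising) = Σ over x = 3 to 27 of P(X1 = x) · P(X2 ≥ 7 − x). This is 0.0977 at p = 0.10 and 0.9001 at p = 0.25, in agreement with the stated 0.1 and 90%.

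The design is correct for whatever response is counted, and what is counted is the four-part composite.

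**2. False-positive rate for CR+CRp.** Set true CR+CRp at 10%, so the composite rate is 10% + d. Any trial in which CR+CRp alone passes both bounds also passes on the composite. So, given a promising result, the chance that CR+CRp alone would have failed is 1 − 0.0977 / P(promising).

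| d (points) | Composite rate | P(promising) | CR+CRp alone fails, given promising |
|---|---|---|---|
| 0 | 10% | 0.098 | 0 |
| 2 | 12% | 0.195 | 0.498 |
| 5 | 15% | 0.388 | 0.748 |
| 10 | 20% | 0.708 | 0.862 |

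**3. Power for CR+CRp.** CR+CRp is a subset of the composite. If the true Cycle 1 CR+CRp rate is 25%, the composite rate is at least 25% and P(promising) is at least 0.90. In the same way, 2 or fewer composite responses in 27, or 6 or fewer in 40, means no more than that many CR+CRp responses. A negative result carries over.

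**4. Rule against interval.** Take an extreme case: seven marrow clearances and no CR or CRp, with at least three of the seven in the first 27 patients. The rule is passed at 7/40. The interval depends on how PR is read (exact Clopper-Pearson limits):

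- None of the seven is PR: 0/40, upper limit 1 − 0.025^(1/40) = 0.088, so 0 to 8.8%.
- A 50% blast decrease alone is PR and all seven meet it: 7/40 = 17.5%, 7.3 to 32.8%.

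On the second reading, rule and interval coincide. The gap between objective and rule remains on either reading.

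**The case against.** The strongest reply is that the composite was intended. Section IV.A lists the same four categories as examples of clinical benefit, and footnote 10 of the Section XII schedule repeats them: "If patient is found to be CR, CRp, PR or marrow clearance of blasts, may receive up to 2 additional cycles". A go/no-go rule on a broad activity endpoint, with CR and CRp reported descriptively, is a possible phase 2 design. Section I says only that the rates will be assessed and states no hypothesis. On this view the missing fourth term in the closing paragraph of Section XX is a drafting slip, and 0.708 at a 20% composite rate is simply how the rule behaves on its own endpoint.

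Much of this stands. It favours keeping the composite, and it shows that 0.708 is an error only if promising is taken to refer to CR+CRp. But the protocol nowhere says that the composite stands in for the primary objective, so a reader of the objectives will take the verdict that way.

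A reader might also infer that the rule gives no error control of any kind for the primary objective, or that the design was miscalculated. The documents support neither. Step 3 shows that power and negative conclusions carry over to CR+CRp, and step 1 reproduces the stated figures. The 0/40 against 7/40 contrast is likewise an extreme case on one reading of PR. It does not show that rule and interval must disagree.

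**Conclusion.** The concern holds for false-positive control only. The stated error rates (exact 0.098 and 0.900) belong to the Cycle 1 composite. For CR+CRp the rule sets no type I error limit: at a true CR+CRp rate of 10%, the chance of a promising verdict is 0.098 with no additional responders and 0.195, 0.388 or 0.708 with 2, 5 or 10 points of them. Those increments are assumptions. Separately, the only planned interval may describe a different endpoint from the one decided on; the size of that gap depends on the PR wording and can be zero. The mismatch touches the primary objective, the futility stop and the final conclusion, so it should be corrected.

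**What to change.** Use one response definition for the decision rule and its interval.

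**Simplest form.**

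- Name the Cycle 1 composite as the primary efficacy endpoint in Section I and the synopsis.
- State that 10% and 25% refer to it, and give their basis. The historical figure in Section II (less than 10% to 20%) does not say which responses it counts.
- Compute the Section XX interval on the composite, and report CR+CRp with its own 95% interval.
- State that a promising result is not an error-controlled conclusion about CR+CRp.

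Cost: wording only, but the primary objective becomes broader than CR/CRp.

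**Alternative.** Apply 2/27 and 6/40 to CR+CRp, with the composite as a secondary rate. The sample size stays at 40. If the composite rate is 25%, P(promising) falls from 0.90 to 0.71 with CR+CRp at 20% and to 0.39 at 15%, and early stopping rises from 0.02 to 0.07 and 0.21.

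**Under either form.**

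- Keep the window that Section XX already sets. A repeated or delayed assessment before Cycle 2 starts still counts as Cycle 1; only responses first seen after Cycle 1 are reported separately. No added assessment is needed.
- State which Section XIII categories count as marrow clearance in the analysis. The sponsor must reconcile the PR wording there with Section IV.A and footnote 10 of Section XII; no PR rule is proposed here.

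**Timing.** Make the change before responses are tabulated if that is still possible. At Amendment 6 of an open-label trial it may not be. In that case keep the composite for the decision, report all three rates with intervals, and disclose when the definition was fixed.

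### The listed toxicity stopping boundaries do not follow from the stated posterior rule: at 4/8, 9/21, 12/29 and 13/32 the rule stops the trial and the list continues

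*Combined protocol and SAP*

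**What the plan says.** Section XX describes the safety monitoring as "A Bayesian sequential monitoring method". It fixes every input:

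- **Limit and cut-off:** stop if the posterior probability of a toxicity rate above 33% exceeds 0.80.
- **Prior:** Beta(0.67, 1.33).
- **Maximum sample size:** 40.

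The boundaries are presented as a consequence of these inputs: "Following this rule, the trial will be terminated due to toxicity if" the ratio of toxicities to evaluated patients reaches one of "2/3, 3/5, 4/7, 5/10, 6/13, 7/15, 8/18, 9/20, 10/23, 11/26, 12/28, 13/31, 14/34, 15/37", or 16/40. The section gives no schedule of looks and does not say whether the formula or the list takes precedence.

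**The concern.** A boundary of this kind is deterministic. Given the prior, the limit and the cut-off, each number of toxic events has one largest number of evaluated patients at which the trial must stop. The list appears to give those largest numbers, and 11 of its 15 entries are exactly that. The other four are one patient too small.

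All four errors run in the same direction: the list lets the trial continue where the rule stops it. The earliest case is patient 8 with four toxic events, when half the evaluated patients have had one. Someone applying the printed list and someone computing the posterior would then reach opposite decisions on the same data, under the only quantitative toxicity stopping rule in the protocol.

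**Working it through.** **Inputs** (all from Section XX): prior Beta(0.67, 1.33), limit 0.33, cut-off 0.80, up to 40 patients.

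**Formula.** After t toxic events in n evaluated patients the posterior is Beta(0.67 + t, 1.33 + n − t). The rule stops the trial if

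P(θ > 0.33 | t, n) = 1 − F(0.33; 0.67 + t, 1.33 + n − t) > 0.80,

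where F is the beta distribution function. For 4 events in 8 patients the posterior is Beta(4.67, 5.33), and its upper tail at 0.33 is 0.8054.

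**Reproducing the list.** An entry t/n is right if the posterior is above 0.80 at n and not above 0.80 at n + 1.

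| Listed t/n | Posterior at n | Posterior at n + 1 | Matches rule? |
|---|---|---|---|
| 2/3 | 0.8193 | 0.7022 | yes |
| 3/5 | 0.8492 | 0.7618 | yes |
| 4/7 | 0.8734 | **0.8054** | no: 4/8 |
| 5/10 | 0.8388 | 0.7755 | yes |
| 6/13 | 0.8127 | 0.7535 | yes |
| 7/15 | 0.8428 | 0.7923 | yes |
| 8/18 | 0.8241 | 0.7757 | yes |
| 9/20 | 0.8506 | **0.8085** | no: 9/21 |
| 10/23 | 0.8361 | 0.7951 | yes |
| 11/26 | 0.8234 | 0.7836 | yes |
| 12/28 | 0.8477 | **0.8123** | no: 12/29 |
| 13/31 | 0.8371 | **0.8023** | no: 13/32 |
| 14/34 | 0.8275 | 0.7934 | yes |
| 15/37 | 0.8188 | 0.7853 | yes |
| 16/40 | 0.8109 | beyond 40 patients | yes |

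All 15 listed points satisfy the rule, so the list never stops the trial where the rule would not. Comparing the two at every n from 1 to 40, they differ only at n = 8, 21, 29 and 32. There the rule needs 4, 9, 12 and 13 events, and the list needs 5, 10, 13 and 14.

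**Could another limit or cut-off explain the list?**

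- *Limit 0.33, any cut-off.* The unlisted point 12/29 (0.8123) has a higher posterior than the listed point 16/40 (0.8109). No cut-off can include the second and exclude the first.
- *Limit 1/3, cut-off 0.80.* 4/8 (0.7991), 9/21 (0.7990) and 13/32 (0.7905) fall below 0.80, so those three listed entries become correct. But 12/29 (0.8014) still stops, and the listed 16/40 (0.7981) no longer does. Thirteen of 15 entries match.
- *Limits from 0.25 to 0.40, any cut-off, stated prior.* No pair reproduces the whole list.

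**Effect on stopping.** Exact recursion, with a look after each patient and the list read as t or more events in n or fewer patients:

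| True toxicity | By patient 8: list / rule | By patient 10: list / rule | By patient 40: list / rule |
|---|---|---|---|
| 20% | 0.125 / 0.138 | 0.134 / 0.141 | 0.147 / 0.155 |
| 33% | 0.328 / 0.374 | 0.373 / 0.393 | 0.528 / 0.545 |
| 40% | 0.460 / 0.523 | 0.530 / 0.552 | 0.781 / 0.793 |
| 50% | 0.648 / 0.723 | 0.740 / 0.759 | 0.969 / 0.971 |

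At 33% true toxicity the expected number of patients, up to 40, is 23.9 under the list and 23.2 under the rule.

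**The case against.** The strongest objection is that 33% may be a rounded 1/3. The prior looks like Beta(2/3, 4/3), which has mean 1/3, and at 1/3 three of the four discrepancies vanish, including the one at patient 8. That may well be how the list arose, but it is an inference. Section XX prints 33%, and at 1/3 two entries are still wrong, 12/28 and 16/40. The second matters little, because all 40 patients are enrolled by then.

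If toxicity were reviewed only at the listed sample sizes, rule and list would agree at every look. But the text describes sequential monitoring and names no such looks, and most of the listed sample sizes are exactly the largest n for each event count.

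If the entries were read as bare ratios, 4/8 would equal 5/10 and so be covered. The points 9/21, 12/29 and 13/32 would not be. Bare ratios are also unworkable: 16/40 is 0.40, so 2 events in 5 patients would stop the trial.

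The objection on size largely stands. Each discrepancy is one patient. The gap of 6 to 7 percentage points at patient 8 (true rates 40% and 50%) shrinks to about 2 points by patient 10. By patient 40 it is at most 1.7 points at the rates examined. Nor do the documents say that staff would work from the list and not the formula.

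**Conclusion.** The list is wrong as written. With the printed prior, limit and cut-off, four of the 15 boundaries are one patient too small, and each error favours continuing. This follows exactly from Section XX's own inputs and needs no outside figure.

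The long-run effect is small: stopping by patient 40 falls from 0.545 to 0.528 at 33% true toxicity and from 0.793 to 0.781 at 40%. The largest effect is at patient 8. These probabilities assume a look after every evaluated patient and the list read as t or more events in n or fewer patients. The size of the error also depends on taking 33% as 0.33. With 1/3 there are two wrong entries in place of four, so the list fails on either reading. The design is not invalidated, but a safety boundary and the rule it is said to come from should not disagree, and this one should be corrected.

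**What to change.** Make the rule and the list agree:

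1. State the toxicity limit exactly (0.33 or 1/3) and regenerate the list from the formula.
   - With 0.33, as printed, four entries change: 4/7 becomes 4/8, 9/20 becomes 9/21, 12/28 becomes 12/29 and 13/31 becomes 13/32.
   - With 1/3, two entries change: 12/28 becomes 12/29, and 16/40 becomes 16/39.
2. Say that each entry means t or more toxic events among n or fewer evaluated patients, and that the posterior is checked after each evaluated patient. If looks are less frequent, give the schedule.
3. Say that the posterior formula governs if it and the list ever differ. If the list was intended to govern, the stated rule has to be rewritten, since no limit and cut-off tried with the stated prior reproduces it.

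The cost is a few corrected numbers and two sentences. With 0.33, the chance of stopping at a true toxicity of 20% rises from 0.147 to 0.155, which the stated rule already implies.
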